9.7. Safety Evaluations

The study will include the following evaluations of safety and tolerability according to the time points provided in the [Time and Events Schedule](#): adverse event reporting, clinical laboratory tests (including biochemistry, hematology, urinalysis, and urine chemistry), vital signs, and physical examinations (complete or symptom-directed). These protocol procedures are described below. In addition to these measurements, guidelines for the management of toxicities are described in Section [9.8](#).

Any clinically relevant changes occurring during the study must be recorded on the Adverse Event section of the eCRF.

Clinical events and clinically significant laboratory abnormalities will be graded according to the Division of AIDS (DAIDS) Table for Grading the Severity of Adult and Pediatric Adverse Events located in [Attachment 2](#).

Any evaluations showing abnormal results at any time during the study will be followed until satisfactory clinical resolution or stabilization. All grade 3 and grade 4 laboratory abnormalities and all laboratory abnormalities resulting in an increase of 2 DAIDS grades from baseline will be followed until return to baseline or within 1 grade from baseline (ie, \leq grade 2) (see Section [9.8.1](#), General Guidance for the Management of Clinical Events and Laboratory Abnormalities).

Evaluations at the ESTD visit showing abnormal results indicating a possible causal relationship with the study treatment must be followed by the investigator (as often as deemed prudent) until

satisfactory clinical resolution or stabilization. Certain long-term adverse events of ART cannot be followed to resolution within the setting of this protocol; in these cases, follow-up will be the responsibility of the treating physician, which will be agreed upon with the sponsor's medical monitor.

Adverse Events

Adverse events will be reported by the subject (or, when appropriate, by a caregiver or surrogate) for the duration of the study. Adverse events will be followed by the investigator as specified in Section 12, Adverse Event Reporting.

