11.8. Safety Analyses

For all safety endpoints listed in Section 2.1.2, descriptive statistics will be used to summarize the endpoints.

Adverse Events

The verbatim terms used in the eCRF by investigators to identify adverse events will be coded using the Medical Dictionary for Regulatory Activities (MedDRA). Treatment-emergent adverse events are adverse events with onset during the treatment phase or that are a consequence of a pre-existing condition that has worsened since baseline. All reported adverse events will be

included in the analysis. For each adverse event, the percentage of subjects who experience at least 1 occurrence of the given event will be summarized.

Summaries, listings, datasets, or subject narratives may be provided, as appropriate, for those subjects who die, who discontinue treatment due to an adverse event, or who experience a severe or life-threatening (grade 3 or 4) or a serious adverse event.

Additionally, a summary and listing of those subjects meeting predefined stopping rules due to safety or resistance findings will be tabulated.

Clinical Laboratory Tests

Abnormalities will be analyzed according to the DAIDS grading table (see [Attachment 2](#)) and in accordance with the normal ranges of the clinical laboratory. Maximum toxicity grades after baseline will be tabulated, and special attention will be given to subjects who develop grade 3 or grade 4 toxicities.

Laboratory data will be summarized by type of laboratory test. Reference ranges and markedly abnormal results (specified in the Statistical Analysis Plan) will be used in the summary of laboratory data. Descriptive statistics will be calculated for each laboratory analyte at baseline and for observed values and changes from baseline at each scheduled time point. Changes from baseline results will be presented in pre- versus posttreatment cross-tabulations (with classes for below, within, and above normal ranges).

Vital Signs

Descriptive statistics of blood pressure (systolic and diastolic), pulse/heart rate, and body weight and changes from baseline will be summarized at each scheduled time point. The percentage of subjects with values beyond clinically important limits will be summarized. See [Attachment 6](#) for the definitions of vital signs abnormalities.

Physical Examination

Descriptive statistics of changes from baseline will be summarized at each scheduled time point.

Patient-reported Outcomes

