Attachment 2: DAIDS Table for Grading the Severity of Adult and Pediatric Adverse Events

The Division of AIDS Table for Grading the Severity of Adult and Pediatric Adverse Events (v 2.0, November 2014), or ‘DAIDS grading table’, is a descriptive terminology to be utilized for adverse event reporting in this study. A grading (severity) scale is provided for each adverse event term.

General InstructionsEstimating Severity Grade for Parameters Not Identified in the Grading Table

If the need arises to grade a clinical adverse event that is not identified in the DAIDS grading table, use the category ‘Estimating Severity Grade’ located at the top of the table on the following page. In addition, all deaths related to an adverse event are to be classified as grade 5.

Grading Adult and Pediatric Adverse Events

The DAIDS grading table includes parameters for grading both adult and pediatric adverse events. When a single set of parameters is not appropriate for grading specific types of adverse events for both adult and pediatric populations, separate sets of parameters for adult and/or pediatric populations (with specified respective age ranges) are provided. If there is no distinction in the table between adult and pediatric values for a type of adverse event, then the single set of parameters listed is to be used for grading the severity of both adult and pediatric events of that type.

Determining Severity Grade

If the severity of an adverse event could fall under either 1 of 2 grades (eg, the severity of an adverse event could be either grade 2 or grade 3), select the higher of the 2 grades for the adverse event.

Laboratory normal ranges should be taken into consideration to assign gradings to a laboratory value.

Definitions

Basic Self-care Functions	Adult Activities such as bathing, dressing, toileting, transfer or movement, continence, and feeding. Young Children Activities that are age and culturally appropriate, such as feeding one’s self with culturally appropriate eating implements.
Usual Social & Functional Activities	Activities which adults and children perform on a routine basis and those which are part of regular activities of daily living, for example: Adults Adaptive tasks and desirable activities, such as going to work, shopping, cooking, use of transportation, or pursuing a hobby. Young Children Activities that are age and culturally appropriate, such as social interactions, play activities, or learning tasks.

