Phosphate, Low (mg/dL; mmol/L) >14 years of age 1 to 14 years of age <1 year of age	2.0 to <LLN 0.81 to <LLN	1.4 to <2.0 0.65 to <0.81	1.0 to <1.4 0.32 to <0.65	<1.0 <0.32
	3.0 to <3.5 0.97 to <1.13	2.5 to <3.0 0.81 to <0.97	1.5 to <2.5 0.48 to <0.81	<1.5 <0.48
	3.5 to <4.5 1.13 to <1.45	2.5 to <3.5 0.81 to <1.13	1.5 to <2.5 0.48 to <0.81	<1.5 <0.48
Potassium, High (mEq/L; mmol/L)	5.6 to <6.0 5.6 to <6.0	6.0 to <6.5 6.0 to <6.5	6.5 to <7.0 6.5 to <7.0	≥7.0 ≥7.0
Potassium, Low (mEq/L; mmol/L)	3.0 to <3.4 3.0 to <3.4	2.5 to <3.0 2.5 to <3.0	2.0 to <2.5 2.0 to <2.5	<2.0 <2.0

¹⁶ Use the applicable formula (Modification of Diet in Renal Disease [MDRD]).¹⁷ Low-density lipoprotein¹⁸ To convert a magnesium value from mg/dL to mmol/L, laboratories should multiply by 0.4114.

CHEMISTRIES				
PARAMETER	GRADE 1 MILD	GRADE 2 MODERATE	GRADE 3 SEVERE	GRADE 4 POTENTIALLY LIFE- THREATENING
Sodium, High (mEq/L; mmol/L)	146 to <150 146 to <150	150 to <154 150 to <154	154 to <160 154 to <160	≥160 ≥160
Sodium, Low (mEq/L; mmol/L)	130 to <135 130 to <135	125 to <130 125 to <135	121 to <125 121 to <125	≤120 ≤120
Uric Acid, High (mg/dL; mmol/L)	7.5 to <10.0 0.45 to <0.59	10.0 to <12.0 0.59 to <0.71	12.0 to <15.0 0.71 to <0.89	≥15.0 ≥0.89

HEMATOLOGY				
PARAMETER	GRADE 1 MILD	GRADE 2 MODERATE	GRADE 3 SEVERE	GRADE 4 POTENTIALLY LIFE- THREATENING
Absolute CD4⁺ Count, Low (cell/mm ³ ; cells/L) >5 years of age (not HIV infected)	300 to <400 300 to <400	200 to <300 200 to <300	100 to <200 100 to <200	<100 <100
Absolute Lymphocyte Count, Low (cell/mm ³ ; cells/L) >5 years of age (not HIV infected)	600 to <650 0.600×10 ⁹ to <0.650×10 ⁹	500 to <600 0.500×10 ⁹ to <0.600×10 ⁹	350 to <500 0.350×10 ⁹ to <0.500×10 ⁹	<350 <0.350×10 ⁹
Absolute Neutrophil Count (ANC), Low (cells/mm ³ ; cells/L) >7 days of age 2 to 7 days of age ≤1 day of age	800 to 1,000 0.800×10 ⁹ to 1.000×10 ⁹ 1,250 to 1,500 1.250×10 ⁹ to 1.500×10 ⁹ 4,000 to 5,000 4.000×10 ⁹ to 5.000×10 ⁹	600 to 799 0.600×10 ⁹ to 0.799×10 ⁹ 1,000 to 1,249 1.000×10 ⁹ to 1.249×10 ⁹ 3,000 to 3,999 3.000×10 ⁹ to 3.999×10 ⁹	400 to 599 0.400×10 ⁹ to 0.599×10 ⁹ 750 to 999 0.750×10 ⁹ to 0.999×10 ⁹ 1,500 to 2,999 1.500×10 ⁹ to 2.999×10 ⁹	<400 <0.400×10 ⁹ <750 <0.750×10 ⁹ <1,500 <1.500×10 ⁹

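### The two unit lines of the low-sodium grade 2 cell in Attachment 2 contradict each other, and the mmol/L line overlaps the whole of grade 1

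*Protocol*

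**What the plan says.** Attachment 2 of the Protocol lists, for each chemistry analyte, limits for grades 1 to 4. For sodium each cell carries two lines, in the order given by the row label "Sodium, Low (mEq/L; mmol/L"): mEq/L first, then mmol/L. The low-sodium cells read:

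- Grade 1: "130 to <135 130 to <135"
- Grade 2: "125 to <130 125 to <135"
- Grade 3: "121 to <125 121 to <125"
- Grade 4: 120 or below in both lines

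The high-sodium row repeats the same numbers in both lines throughout; its grade 2 cell, for example, is "150 to <154 150 to <154".

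Three other places use these grades. The general instructions at the head of Attachment 2 say that where severity could fall under either of two grades, one should "select the higher of the 2 grades for the adverse event". Section 9.7 says that "all laboratory abnormalities resulting in an increase of 2 DAIDS grades from baseline will be followed" until they return to baseline or to within one grade of it. Section 11.8 analyzes laboratory abnormalities by this table and states that "Maximum toxicity grades after baseline will be tabulated". Sodium is in the serum chemistry panel of Section 9.7, and the Time and Events Schedule has chemistry drawn at baseline and at Weeks 2, 4, 8, 12, 24, 36 and 48.

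**The concern.** A grading scale must place each value in one grade. In mEq/L the low-sodium bands meet without overlap. In mmol/L the upper limit of grade 2 is the same as the upper limit of grade 1, so grade 1 lies wholly inside grade 2. The table treats the two units as interchangeable for sodium, so one cell cannot properly carry two different upper limits.

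What depends on it is the boundary between grades 1 and 2 for mild low sodium. That boundary feeds the maximum-toxicity table and the trigger of the two-grade rule. The Protocol does not say which of the two lines the grading program applies.

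**Working it through.** **Inputs.** All limits are from Attachment 2 (Chemistries, Sodium High and Sodium Low). The tie rule is from the general instructions of Attachment 2, and the two-grade rule is from Section 9.7.

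**Step 1: are the units interchangeable in the table?** There are eight sodium cells (four grades, high and low). Seven have identical limits in both lines. The exception is low sodium, grade 2, where the upper limits are 130 and 135.

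**Step 2: do adjacent bands meet?** For a low-value scale, the upper limit of each grade should equal the lower limit of the next milder grade.

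| Boundary (low sodium) | mEq/L | mmol/L |
|---|---|---|
| Grade 2 upper vs grade 1 lower | 130 = 130, meets | 135 vs 130, overlap of 5 units |
| Grade 3 upper vs grade 2 lower | 125 = 125, meets | 125 = 125, meets |

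The high-sodium bands also meet at both checked boundaries (150 and 154). The only failure is the grade 1/2 boundary in the low-sodium mmol/L line.

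**Step 3: grade whole-number values under each line.**

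| Sodium | mEq/L line | mmol/L line, bands that fit | mmol/L, higher taken |
|---|---|---|---|
| 135 and 136 | none | none | 0 |
| 130, 131, 132, 133, 134 | 1 | 1 and 2 | 2 |
| 125 to 129 | 2 | 2 | 2 |
| 121 to 124 | 3 | 3 | 3 |
| 120 or below | 4 | 4 | 4 |

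Only 130 to 134 differs. With the tie rule applied, no mmol/L value can be grade 1.

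**Step 4: the two-grade rule from a grade 0 baseline.** For 130 to 134 the rise is 1 − 0 = 1 grade on the mEq/L line and 2 − 0 = 2 grades on the mmol/L line. The rule is nominally met only on the mmol/L line.

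**Step 5: effect of removing the overlap.** With 125 to <130 on both lines, 130 to 134 is grade 1 only, the rise from grade 0 is one grade, and no other graded value changes.

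**How many subjects could be regraded?** The Protocol gives no sodium distribution, so any figure is an assumption. Take a normal distribution, values rounded to whole units and seven post-baseline draws. The share of readings at 130 to 134 is approximately Φ((134.5 − mean)/total SD), where total SD = √(between-subject² + within-subject²).

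| Assumed mean; between SD, within SD | Total SD | z | Readings at 130-134 | Subjects with at least one | Same, starting from a normal baseline |
|---|---|---|---|---|---|
| 140; 1.5, 1.8 | 2.34 | −2.35 | about 0.9% | about 5% | about 5% |
| 139.5; 1.5, 2.0 | 2.50 | −2.00 | about 2.3% | about 12% | about 11% |
| 139; 1.8, 2.0 | 2.69 | −1.67 | about 4.7% | about 20% | about 17% |

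The last two columns come from simulation of 400,000 subjects. They apply only if the mmol/L line is the one programmed and the tie rule is applied to laboratory values. If the mEq/L line is used, the number is zero.

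**The case against.** The mismatch on the page is not disputed. The case on the other side concerns its consequences, and most of it stands.

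- **Follow-up.** A reader might infer that the error imposes extra follow-up. The documents do not support that in practice. Section 9.7 already has any abnormal result followed to resolution or stabilization, whatever its grade. It also glosses the end of the two-grade rule as grade 2 or below, so on that gloss a grade 2 sodium meets the end condition when it is found. The gloss sits awkwardly with a grade 0 baseline, but it leaves little that the regrading would add.
- **Treatment rules, alerts and endpoint.** Section 9.8.1 handles grades 1 and 2 alike. Laboratory alerts and confirmatory retests (Section 9.7) start at grade 3, and the laboratory safety endpoint in Section 2.1.2 is grade 3 and 4. Grades 3 and 4 agree in both units, so none of these is touched.
- **Different handling within the trial.** A reader might infer that the same sodium would be graded differently from one subject to another. Section 9.7 sends all clinical laboratory testing to the central laboratory, so mixed units are unlikely. The open question is which single line that laboratory applies.
- **The tie rule.** It is worded for adverse events, and Section 12.1.3 says laboratory abnormalities are usually not recorded as such. If it does not apply, 130 to 134 mmol/L has no unique grade rather than being grade 2. That softens the consequence but does not remove the contradiction.
- **A copying fault.** A one-digit fault in the copy at hand cannot be wholly excluded. The row is otherwise complete and aligned, so this is not the likelier explanation, but the issued page should be checked.

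**Conclusion.** The contradiction holds: one cell states two different upper limits for grade 2 low sodium, against seven sodium cells that agree across units, and the mmol/L line overlaps all of grade 1. Its reach is narrow. Values of 130 to 134 could be tabulated as grade 2 instead of grade 1, and could nominally satisfy the two-grade rule from a grade 0 baseline. Both depend on the mmol/L line being used as printed and on the tie rule being applied.

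The result is a possible shift between two mild grades in a descriptive table of a single-arm study with no hypothesis test. The range of about 5% to 20% of subjects should not be read as an expected effect. It rests on assumed sodium distributions and on the mmol/L line being programmed, and it does not measure the two-grade rule, which also needs a grade 0 baseline. This is a minor correction, worth making because it is certain on the page and nearly free.

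**What to change.** Reconcile the two unit lines of the low-sodium grade 2 cell so that they state the same limits, as every other sodium cell does, and so that grades 1 and 2 do not overlap. Check the cell against the source table from which Attachment 2 was taken. Then confirm in writing that the central laboratory's grading program, and the program for the maximum-toxicity table, use the reconciled limits. The cost is one table cell at the next amendment and one check of the programmed limits. No visit, sample or endpoint changes.

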APPENDIX A: TOTAL BILIRUBIN TABLE FOR TERM AND PRETERM NEONATES

PARAMETER	GRADE 1 MILD	GRADE 2 MODERATE	GRADE 3 SEVERE	GRADE 4 POTENTIALLY LIFE- THREATENING
Total Bilirubin ¹⁹ , High (mg/dL; $\mu\text{mol/L}$) ²⁰				
Term Neonate ²¹				
<24 hours of age	4 to <7 68.4 to <119.7	7 to <10 119.7 to <171	10 to <17 171 to <290.7	≥ 17 ≥ 290.7
24 to <48 hours of age	5 to <8 85.5 to <136.8	8 to <12 136.8 to <205.2	12 to <19 205.2 to <324.9	≥ 19 ≥ 324.9
48 to <72 hours of age	8.5 to <13 145.35 to <222.3	13 to <15 222.3 to <256.5	15 to <22 256.5 to <376.2	≥ 22 ≥ 376.2
72 hours to <7 days of age	11 to <16 188.1 to <273.6	16 to <18 273.6 to <307.8	18 to <24 307.8 to <410.4	≥ 24 ≥ 410.4
7 to 28 days of age (breast feeding)	5 to <10 85.5 to <171	10 to <20 171 to <342	20 to <25 342 to <427.5	≥ 25 ≥ 427.5
7 to 28 days of age (not breast feeding)	1.1 to <1.6 \times ULN	1.6 to <2.6 \times ULN	2.6 to <5.0 \times ULN	$\geq 5.0\times$ ULN
Preterm Neonate ²¹				
35 to <37 weeks gestational age	Same as for Total Bilirubin, High, Term Neonate (based on days of age).	Same as for Total Bilirubin, High, Term Neonate (based on days of age).	Same as for Total Bilirubin, High, Term Neonate (based on days of age).	Same as for Total Bilirubin, High, Term Neonate (based on days of age).
32 to <35 weeks gestational age and <7 days of age	NA	NA	10 to <14 171 to <239.4	≥ 14 ≥ 239.4
28 to <32 weeks gestational age and <7 days of age	NA	NA	6 to <10 102.6 to <171	≥ 10 ≥ 171
<28 weeks gestational age and <7 days of age	NA	NA	5 to <8 85.5 to <136.8	≥ 8 ≥ 136.8
7 to 28 days of age (breast feeding)	5 to <10 85.5 to <171	10 to <20 171 to <342	20 to <25 342 to <427.5	≥ 25 ≥ 427.5
7 to 28 days of age (not breast feeding)	1.1 to <1.6 \times ULN	1.6 to <2.6 \times ULN	2.6 to <5.0 \times ULN	$\geq 5.0\times$ ULN

¹⁹ Severity grading for total bilirubin in neonates is complex, because of rapidly changing total bilirubin normal ranges in the first week of life followed by the benign phenomenon of breast milk jaundice after the first week of life. Severity grading in this appendix corresponds approximately to cut-offs for indications for phototherapy at grade 3 and for exchange transfusion at grade 4.

²⁰ A laboratory value of 1 mg/dL is equivalent to 17.1 $\mu\text{mol/L}$.

²¹ Definitions: Term is defined as ≥ 37 weeks gestational age; near-term, as ≥ 35 weeks gestational age; preterm, as <35 weeks gestational age; and neonate, as 0 to 28 days of age.

Attachment 3: WHO Clinical Staging of HIV/AIDS

The clinical stages of HIV infection for adults and adolescents are defined as follows. (Adapted from: 1993 Revised classification system for HIV infection and expanded surveillance case definition for AIDS among adolescents and adults. MMWR 1992;41(RR-17):1-19; and WHO 2007 Case definitions of HIV for surveillance and revised clinical staging and immunological classification of HIV-related disease in adults and children [Table 3]).^{31,42}

Clinical Stage 1

Clinical Stage 1 consists of one or more of the conditions listed below in adolescents or adults (≥ 13 years) with documented HIV infection. Conditions listed in Clinical Stages 2, 3 or 4 must not have occurred.

- Asymptomatic HIV infection
- Persistent generalized lymphadenopathy

Clinical Stage 2

Clinical Stage 2 consists of symptomatic conditions in an HIV-infected adolescents or adults that are not included among conditions listed in Clinical Stage 3, and that meet one or more of the following criteria: a) the conditions are attributed to HIV infection or are indicative of a defect in cell-mediated immunity; or b) the conditions are considered by physicians to have a clinical course or to require management that is complicated by HIV infection. Examples of conditions in Clinical Stage 2 include, but are not limited to the following.

- Moderate unexplained weight loss ($< 10\%$ of presumed or measured body weight)
- Recurrent respiratory tract infections sinusitis, tonsillitis, otitis media and pharyngitis)
- Herpes zoster
- Angular cheilitis
- Recurrent oral ulceration
- Papular pruritic eruptions
- Seborrhoeic dermatitis
- Fungal nail infections

Clinical Stage 3

[figure not shown]
Clinical Stage 3 includes the clinical conditions listed in the AIDS surveillance case definition. For classification purposes, once a Clinical Stage 3 condition has occurred, the person will remain in Clinical Stage 3. Conditions in Clinical Stage 3 include the following.

- Unexplained (not explained by other causes) severe weight loss ($> 10\%$ of presumed or measured body weight)
- Unexplained chronic diarrhea for longer than 1 month
- Unexplained persistent fever (above 37.6°C intermittent or constant, for longer than 1 month)
- Persistent oral candidiasis
- Oral hairy leukoplakia
- Pulmonary tuberculosis (current)
- Severe bacterial infections (such as pneumonia, empyema, pyomyositis, bone or joint infection, meningitis or bacteremia)
- Acute necrotizing ulcerative stomatitis, gingivitis or periodontitis
- Unexplained anemia (< 8 g/dL), neutropenia ($< 0.5 \times 10^9/\text{L}$) or chronic thrombocytopenia ($< 50 \times 10^9/\text{L}$)

Clinical Stage 4

HIV wasting syndrome:

- Pneumocystis pneumonia
- Recurrent severe bacterial pneumonia
- Chronic herpes simplex infection (orolabial, genital or anorectal of more than one month's duration or visceral at any site)
- Esophageal candidiasis (or candidiasis of trachea, bronchi or lungs)
- Extrapulmonary tuberculosis
- Kaposi's sarcoma
- Cytomegalovirus infection (retinitis or infection of other organs)
- Central nervous system toxoplasmosis
- HIV encephalopathy
- Extrapulmonary cryptococcosis including meningitis
- Disseminated non-tuberculous mycobacterial infection
- Progressive multifocal leukoencephalopathy
- Chronic cryptosporidiosis (with diarrhea)
- Chronic isosporiasis
- Disseminated mycosis (coccidiomycosis or histoplasmosis)
- Recurrent non-typhoidal Salmonella bacteremia
- Lymphoma (cerebral or B-cell non-Hodgkin) or other solid HIV-associated tumors
- Invasive cervical carcinoma
- Atypical disseminated leishmaniasis
- Symptomatic HIV-associated nephropathy or symptomatic HIV-associated cardiomyopathy

Attachment 4: Management of Clinically Significant Laboratory Toxicities*

^a Mandatory confirmation is not warranted for asymptomatic grade 3 or grade 4 glucose elevations in subjects with pre-existing diabetes, and asymptomatic grade 3 or grade 4 triglyceride or cholesterol elevations.

*** Please note that this Attachment does not apply to screening/baseline eGFR, AST, ALT, and lipase, and does also not apply to the allowed retesting of abnormal screening/baseline eGFR, AST, ALT, and lipase values (see Section 3.1).**

